7.4. Statistical methodology for safety

Descriptive statistics, tabulation and graphic representation will be used for the evaluation of safety for this phase II study, as described in Section 12 (Appendix III) and Section 13 (Appendix IV).

7.4.1. Exposure

Cumulative dose, dose intensity and relative dose intensity, cycle delay, and dose modifications or omissions will be described following standard tables detailed in Section 12.1 (Appendix III).

7.4.2. Cycle delays, skipped doses and dose modifications

Patients who receive only one infusion of Zalypsis[®] and have treatment discontinuation within the first cycle due to any reason different from drug related adverse event (eg: disease progression, patient's refusal), will not be considered for the calculations of the number of dose administration delays, doses skipped or dose reductions.

Dose delay is defined by a delay in the administration of the first infusion of one cycle (Day 1 infusion). Infusions not administered on Days 8 and/or 15 of the cycle are considered skipped doses and are analyzed separately.

The item "Dose delayed: No/Yes" in the case report form (CRF) will be used to calculate the delay. For doses considered as delayed by the investigator, the delay will be calculated as:

Administration delay (in days) will be equal to the date of start of the actual cycle minus the date of start of previous cycle minus 28 days (planed cycle duration, in days).

A second analysis taking into account the drug administration dates rather than the item "dose delay" completed by the investigator will be performed in order to know the calculated delay in days.

The first cycle is excluded from all calculation of cycle delay (and the denominator used for calculations will be equal to the number of cycles susceptible to be delayed).

The distribution of delays will be studied by means of counts and percentages (the denominator used for calculations will be equal to the number of patients/cycles susceptible of delay). The reasons for infusion delay will be detailed, specifying how many were due to treatment and how many were not. Within delays attributable to treatment, hematological and non-hematological reasons will be outlined, and the specific reasons will be detailed (administrative reasons will be analyzed separately and additional tables will be prepared after exclusion of those delays).

Skipped dose or dose omission is defined as every infusion not administered on Day 8 and/or 15 of the cycle. The distribution of skipped doses will be studied by means of counts and percentages (the denominator used for calculations will be equal to the number of patients/cycles susceptible to have an omission) and a detailed listing of patients with skipped

dose and reason will be showed. Also reasons for dose omission will be detailed, specifying how many were due to treatment and how many were not.

Dose reduction refers to any dose modification occurred after the first drug administration. The distribution of reductions will be studied by means of counts and percentages (the denominator used for calculations will be equal to the number of patients/cycles susceptible to be reduced). All dose reductions will be considered and described (per cycle and patient), specifying the magnitude and the reason for reduction (hematological toxicity, non-hematological toxicity or other causes not due to treatment).

7.4.3. Adverse events

Adverse events (AEs) will be graded according to NCI-CTCAE v4.0 and will be coded using the MeDRA, v11.0. The incidence and grade of AEs and laboratory abnormalities will be calculated considering the most severe grade per patient and cycle. The numeric form of the NCI-CTCAE grade (Grade 0, 1, 2, 3, 4, 5) will be used for all tables and listings. Grades displayed in tables and figures will be grouped in categories to simplify reading (occurrence of grade 5 of the NCI-CTCAE will be in tables indicated by Grade 4* and the asterisk (*) will have associated with a footnote where further detail information is provided). Totals will be provided in all tables.

As far as all the events and abnormalities are concerned, the NCI-CTCAE grade will be used wherever an NCI-CTCAE grading exists. Otherwise, the severity will be noted. As a convention, the term "Grade" will always be used. Toxicities will be described according to the worst NCI-CTCAE grade reported or, for toxicities which do not form the subject of NCI-CTCAE classification, according to the worst severity.

Descriptive statistics will be used to present the profiles of drug-related AEs, drug-related deaths, SAEs and drug-related treatment discontinuations and the observed grade 1-4 toxicities, per patient and per cycle. The incidence and grade of AEs and laboratory abnormalities will be calculated considering the most severe grade per patient and infusion and will be displayed in frequency tables using counts and percentages.

7.4.4. Deaths and serious adverse events

Database listings of deaths and serious adverse events will be provided, including at least date of onset and resolution (if applicable), severity, relationship to study drug, significant consequences and action taken. Deaths on treatment (within 30 days from last study drug administration) will also be included.

7.4.5. Laboratory evaluations

Hematology

Hematological abnormalities classified according to the NCI-CTCAE will be calculated in all cycles. The worst grade reached by each patient during treatment will be also calculated.

If serious abnormalities occur, special follow-up including calculation of nadir values and median time to recover to baseline values with 95% confidence intervals (CIs) and descriptive tables will be made to find out the pattern of thrombocytopenia and neutropenia within and between the different cycles.

If appropriate, these tables might be complemented with boxplots for the nadir of neutrophils and platelets count by cycle along the treatment. Furthermore, graphs of the inter-cycle time course of neutropenia and thrombocytopenia will be provided. Graphs comparing the time course during the first and second or further cycles will be created, if required.

Serum Biochemistry

The non-hematological laboratory abnormalities (i.e., NCI-CTCAE grades) of transaminases, creatinine, creatine phosphokinase (CPK), bilirubin, alkaline phosphatase (AP), etc., by patient

and cycle, will be calculated as explained for hematological disorders. The worst grade reported for each patient during treatment be recorded.

If appropriate, the time to onset and recovery from selected non-hematological abnormalities (i.e., hepatic enzymes) will be illustrated graphically and by means of descriptive statistics.

Shift from baseline

The shift of severity grades from baseline to the worst occurrence during treatment will be tabulated. The time to onset and recovery from neutrophils, platelets, and hepatic enzymes elevations will be illustrated by means of descriptive statistics.

7.4.6. Other safety evaluations

Physical examination evaluation (normal/abnormal) and vital signs at baseline and during treatment will be described by means of frequency counts and summary statistics.

Electrocardiogram (ECG) evaluation (normal/abnormal) will be summarized with frequency counts

Continuous variables (LVEF and LVEF Normal Range) will be summarized and presented with summary statistics, i.e., mean, standard deviation, median and range.

Tabulation of baseline values and evolution during treatment will be presented for PS, weight, and LVEF, troponin I measurement.

7.4.7. Concomitant Medication

Concomitant therapies will be categorized per the World Health Organization Anatomical Therapeutic Chemical (WHO-ATC) class and coded term. The number of patients receiving each type of therapy during the treatment phase will be tabulated in two separate tables: a frequency tabulation of the different therapies that started pre-study, and a frequency tabulation of the different therapies that started during the study. Each table will be generated by system, indication and agent family, WHO-ATC levels 1, 2 and 4 and once by coded term. The accompanying listing will contain all concomitant therapies.

See Section 12.2-12.5 (Appendix III) for further details on the safety analysis.

7.5. Pharmacokinetic (PK), Pharmacodynamic profile and pharmacogenomic (PGx) evaluation

These analyses will be described in two different documents not included in this SAP.

8. Other statistical analysis considerations

8.1. Missing value management

In case of missing values in the determination of protocol deviations (for instance, time from last anticancer treatment to start of treatment with Zalypsis®) the most conservative approach will be taken for the evaluation.

The cycles with missing information regarding laboratory values or adverse events will be subtracted from the denominator of the tables.

8.1.1. Imputation in incomplete dates

Before registration

If the day of a date is unknown (i.e, UK/Jan/09) then the imputed day will be the 15th. If the month is also unknown (i.e, UK/UK/09) then the imputed date will be July 1st. This assumption will be valid if the imputed date is earlier than the informed consent's date. Otherwise the imputed date will be the first day of the informed consent's month date (i.e., 01 / informed consent's month / year).

After end of treatment

To ensure the most conservative approach for the main time-to-event variables (i.e., PFS and OS) that can be affected by missing values, the following rules will be implemented: if the day of a date is unknown then the imputed day will be the 1st; if the month is also unknown, then the imputed date will be July 1st. This assumption will be valid if the imputed date occurs later than the last drug administration date; otherwise the imputed date will be either last drug administration date plus the planed cycle duration (28 days), or the last day of the reported month, whichever occurs first.

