5.2. Secondary endpoints

- Duration of response (DOR): is defined as the time between the date when the response criteria (PR or CR, whichever is reached first) are fulfilled and the first date when disease progression, recurrence or death is objectively documented (taking the smallest measurements documented since the treatment started as reference for PD). DOR censoring rules are the same as for progression-free survival (PFS) and are described below.
- Progression-free survival (PFS): is defined as the time from the date of the first study drug administration to the date of documented progressive disease (PD) by RECIST v1.1 or death (regardless of the cause of death). If the patient receives further antitumor therapy before PD and within the timeframe expected for first follow-up, PFS will be censored on the date of the last disease assessment prior to the administration of this antitumor therapy. If the patient is lost to follow-up for the assessment of progression, or has more than one

missing follow-up between the date of last tumor assessment and the date of progression, death or further antitumor therapy, the PFS will be censored at the date of last valid tumor assessment before the missing evaluations. PFS at three and PFS at six months (PFS3 and PFS6) are defined as the Kaplan Meier estimates of PFS at these time points.

- Overall survival (OS): is defined as the time from the first day of study treatment administration to the date of death (or the last date when the patient is known to be alive). Survival will be followed every three months until death, or until the date of study termination, whichever occurs first. OS at 12 months (OS12) is defined as the Kaplan-Meier estimates of OS at this time point.
- Safety profile: adverse events (AEs), serious adverse events (SAEs), laboratory evaluations, deaths and the reason for study discontinuations, dose delays, modifications or omissions will be analyzed. All AEs and SAEs will be classified according to the NCI-CTCAE, v4.0, and will be coded using the Medical Dictionary for Regulatory Activities (MedDRA).

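### The SAP rule for incomplete post-treatment dates can place a death before a documented contact, and it is not the most conservative rule it claims to be (minor)

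*SAP*

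**What the plan says.** SAP 8.1.1, under the part for dates after end of treatment, gives its purpose as: "To ensure the most conservative approach for the main time-to-event variables", and names PFS and OS. It then sets three steps:

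- Day missing: "if the day of a date is unknown then the imputed day will be the 1st".
- Month missing too: "if the month is also unknown, then the imputed date will be July 1st".
- Check and fallback: "This assumption will be valid if the imputed date occurs later than the last drug administration date"; otherwise the date becomes "last drug administration date plus the planed cycle duration (28 days), or the last day of the reported month, whichever occurs first".

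Neither document compares the imputed date with any contact after the last dose. Such contacts are planned. Protocol 5.8 schedules an end-of-treatment visit 30 days after the last infusion, and protocol 5.9 schedules follow-up every three months. SAP 5.2 already uses the dates that a check would need. OS falls back on "or the last date when the patient is known to be alive". For PFS after missing evaluations, "PFS will be censored at the date of last valid tumor assessment before the missing evaluations"; DOR takes over the PFS censoring rules.

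**The concern.** Two separate problems follow from the text.

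First, the last dose is too early a reference point. A patient can be seen alive weeks or months after it, and the rule can still place the death before that visit. The same section does test imputed pre-registration dates against the informed consent date, so the plan accepts the principle of a plausibility check. After treatment it picks a reference that later data can overtake.

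Second, the section claims to be most conservative. In a single-arm trial that should mean the earliest event date the data allow. The 1st of the month has that property within the month. A mid-year date and a month-end date do not.

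At stake are OS, OS at 12 months, PFS and DOR. Some event times could contradict the database, and the direction of the error would depend on which step of the rule applied.

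**Working it through.** The plan states no figure to reproduce here, so the check applies the rule as written to worked dates and compares it with the earliest compatible date.

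**Inputs.** The three steps come from SAP 8.1.1, the visit at last dose + 30 days from protocol 5.8, three-monthly follow-up from protocol 5.9, and N = 29 (12 in stage 1) from SAP 6.1.

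**Comparator.** Earliest compatible date = max(first day of the reported month or year, last dose + 1 day, last date known alive + 1 day).

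| Case | Last dose | Last known alive | Reported death | SAP date | Earliest compatible |
|---|---|---|---|---|---|
| A | 20 Feb 2012 | 21 Mar 2012 | Mar 2012 | 1 Mar 2012 | 22 Mar 2012 |
| B | 5 Mar 2012 | 20 Sep 2012 | 2012 | 1 Jul 2012 | 21 Sep 2012 |
| C | 5 Jan 2012 | 4 Feb 2012 | 2012 | 1 Jul 2012 | 5 Feb 2012 |
| D | 10 Mar 2012 | 10 Mar 2012 | Mar 2012 | 31 Mar 2012 | 11 Mar 2012 |
| E | 20 Dec 2011 | 20 Dec 2011 | 2011 | 17 Jan 2012 | 21 Dec 2011 |
| F | 1 Aug 2012 | 31 Aug 2012 | 2012 | 29 Aug 2012 | 1 Sep 2012 |

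**Impossible order (A, B, F).** The SAP date precedes a documented contact by 20, 81 and 2 days. In F the fallback does this by itself, because last dose + 28 is two days before a day-30 visit.

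How general is A? Take every last-dose date from 2011 to 2013 (1,096 days), with the visit 30 days later and death later in the visit month. The 36 visits on the last day of a month leave no later day, so 1,096 − 36 = 1,060 positions remain. The imputed 1st precedes the visit in all but the 36 cases where the visit is itself on the 1st: 1,024/1,060 = 97%.

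**Conservatism.**

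- Day missing, check passed: the 1st is never later than the true date, and is 0 to 30 days early.
- Month missing, check passed: 1 July can be up to 182 days after the true date (1 January to 1 July in a leap year) or up to 183 days before it (31 December). In C it is 147 days later than the earliest compatible date.
- Fallback with the month known: month-end is chosen whenever dose day + 28 reaches the end of the month. That holds for 29 of 31, 29 of 30, 29 of 29 or 28 of 28 dose days, by length of month. Month-end is the latest date the report allows; in D it is 20 days later than the earliest.
- Fallback with the month missing: there is no reported month, so the month-end option is undefined. Last dose + 28 then stands alone and can leave the reported year, as in E.

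**Illustrative frequency.** Neither document gives a survival assumption, so this is a range. Assume exponential OS with median 6, 9 or 12 months, last dose 15 to 119 days after the first (at least 31 days before death), and contact kept at day 30 after the last dose and every 91 days thereafter.

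| Missing part | Before last known alive | Later than true date | Crosses 12 months |
|---|---|---|---|
| Day | 25–32% | 0% | 1.5% |
| Day and month | 39–41% | 49–50% | 9–11% |

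The last entry adds both directions: 5.2% + 4.0% = 9.2% at median 12 months, and 6.4% + 4.3% = 10.7% at median 6 months. All percentages are of deaths with an incomplete date, not of all deaths.

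**Weight of one patient.** 1/29 = 3.4 points of OS12, or 1/12 = 8.3 points if the trial stops after stage 1, ignoring censoring.

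**The case against.** The strongest reply is about direction. Dating a death before the last contact shortens survival, so in a single-arm trial it understates benefit. For dates missing only the day and passing the check, the rule is conservative. That stands. It removes any suggestion that the impossible dates flatter the drug, but it does not make those dates acceptable, and it does not rescue 1 July or the fallback.

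The fallback is also narrow. With a known month it applies only when the imputed 1st is not after the last dose, in practice when the event falls in the month of the last dose. It takes the earlier of two dates, and the shift is under a month. That stands too; 1 July is the larger non-conservative element.

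The progression side is weak. Progression is dated from scans every other cycle and then at three-monthly follow-up. Placing a day-missing progression before a clean scan needs two assessments in one month, or a date known only to the year.

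A reader might go further in three ways that the documents do not support:

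- That death dates are the ones most likely to be incomplete. Nothing says so, and SAP Appendix V lists a dedicated death report form.
- That every incomplete date moves OS12 by 3.4 points. Only a shift across 12 months does.
- That counts of deaths within 30 days of the last dose (SAP 7.4.4) are distorted. The rule is written for time-to-event variables, and the SAP does not say imputed dates feed those listings.

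**Conclusion.** The point holds, at minor severity. As written, the rule can produce event dates that the database contradicts, and its claim to be most conservative is wrong for year-only dates and for the fallback. Both conclusions follow from the SAP text and calendar arithmetic and need no survival assumption. The simulated percentages do rest on assumed survival and on visits being kept.

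A reader might infer that the trial's conclusion is at risk. It is not: ORR and the two-stage rule do not use these dates. OS, OS12, PFS and DOR are secondary and described by Kaplan-Meier, and SAP 7.3 makes any test exploratory. The number of incomplete dates is unknown and may be zero, so the statement is that these endpoints could be affected.

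**What to change.** Replace both 1 July and the fallback with one rule. Impute the latest of:

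- the first day of the reported month (or of the reported year if the month is missing);
- the day after the last dose;
- the day after the last date known alive (OS), or after the last assessment without progression (PFS, DOR).

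Keep the result within the reported month or year and the data cutoff. This is the earliest date compatible with the record, so the conservative claim becomes true.

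If the present rule is kept, add the same floor to every step, including the fallback, and delete the claim. The floor alone does not earn it: case C would stay at 1 July and case D at 31 March. A sensitivity run at the latest possible date would not support it either, since that tests the optimistic extreme.

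The cost is a few sentences in SAP 8.1.1 and a short change to the derivation code, using dates already collected.

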8.2. Data analysis conventions

Percentages in the summary tables will be rounded to one decimal unless otherwise specified, and, therefore, may not always add up to exactly 100%.

Calcium can be falsely low if hypoalbuminemia is present. Serum album is <4.0 g/dl, hypocalcemia will be reported after the following correction is performed:

Calcium corrected (mMol/l) = Calcium (mMol/l) + $0.2 \times (4 - \text{Albumin}(g/dl))$

Calcium corrected (g/dl) = Calcium (g/dl) + 0.8 x (4 - Albumin(g/dl))

In case of albumin and calcium results are not performed in the same date then the nearest albumin result to the calcium will be taken and if a calcium result falls at an equal time between two albumin results, then the earlier albumin result will be used for the calculation.

If there is no any albumin results or the result exceeds more than 30 days from calcium result then no correction will be used.

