4. SELECTION OF PATIENTS

4.1. INCLUSION CRITERIA

In order to be included into the trial, patients have to fulfill all of the following criteria:

1. Voluntary written informed consent, obtained from the patient or his/her representative before the beginning of any specific study procedures.
2. Age ≥ 16 years.
3. Histologically or cytologically confirmed EFT, with recurrent disease.
4. Documented failure to at least one prior chemotherapy regimen for their disease.
5. Radiographic documentation of disease progression at study entry.
6. Eastern Cooperative Oncology Group (ECOG) performance status (PS) score ≤ 2 .
7. Life expectancy ≥ 3 months.
8. Complete recovery from the effects of drug-related AEs derived from previous treatments, excluding alopecia and grade 1 peripheral neuropathy, according to the NCI-CTCAE v. 4.0.
9. At least one measurable lesion ("target lesion" according to the RECIST v. 1.1), located in a non-irradiated area and adequately measured less than four weeks before study entry. Tumors within a previously irradiated field will be designated as "non-target" lesions unless progression is clearly documented or biopsy proven.
10. Absolute neutrophil count (ANC) $\geq 1.5 \times 10^9/l$; platelet count $\geq 100 \times 10^9/l$, and hemoglobin ≥ 9 g/dl.
11. Adequate renal function: calculated creatinine clearance (using Cockcroft and Gault's formula) ≥ 30 ml/min.
12. Adequate hepatic function:
 - a) Total bilirubin $\leq 1.5 \times$ upper limit or normality (ULN), unless due to Gilbert's syndrome.
 - b) Alanine aminotransferase (ALT), aspartate aminotransferase (AST) $\leq 3 \times$ ULN ($\leq 5 \times$ ULN in case of hepatic metastases), and alkaline phosphatase (AP) $\leq 2.5 \times$ ULN ($\leq 5 \times$ ULN in case of extensive bone involvement).
 - c) Albumin ≥ 25 g/l.
13. Left ventricular ejection fraction (LVEF) within normal limits (LVEF of at least 50%).
14. Women of childbearing potential must have a negative serum pregnancy test before study entry. Both women and men must agree to use a medically acceptable method of contraception throughout the treatment period and for three months after discontinuation of treatment. Acceptable methods of contraception include complete abstinence, intrauterine device (IUD), oral contraceptive, subdermal implant and double barrier (condom with a contraceptive sponge or contraceptive suppository).

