11.1.7. Biochemical values at baseline

Table 11.1.7.1 Biochemical abnormalities at baseline.

Doromotor*	Gra	Grade 1		de 2	Gra	de 3	Gra	de 4	Total	(G1-G4)
Parameter*	N	%	N	%	N	%	N	%	N	%
AST										
ALT										
*										

(*) Total bilirubin, AP, CPK and Creatinine. All biochemical abnormalities susceptible to be graded in NCI-CTCAE v4.0

Table 11.1.7.2 Biochemistry at baseline. Last value before treatment.

Parameter* Median Min N Max AST ALT Total Bilirubin (*) Units for AST, ALT, AP, CPK are IU/l. Units for Total Bilirubin and Creatinine are mg/dl. Table 11.1.7.3 Biochemistry at baseline. Patients with missing biochemical parameters. Patient ID. **Parameter** Table 11.1.7.4 Biochemistry at baseline. Abnormalities grade ≥ 2 . Patient ID. **Parameter** Value Grade 11.1.8. Other metabolic values at baseline Table 11.1.8.1 Other metabolic abnormalities at baseline (hyper-hypo). Grade 2 Grade 3 Total (G1-G4) Grade 1 Grade 4 Parameter* % N N % N % N % N % Hyperglycemia (*) Hyper and hypo abnormalities and all metabolic parameters susceptible to be graded as per NCI-CTCAE v4.0; i.e, Glucose, Sodium, Potassium, Calcium, Magnesium and Albumin. Table 11.1.8.2 Other metabolic abnormalities at baseline. Last value before treatment. Parameter* Median Min Max Glucose (*) Units for Glucose, Sodium, Clorhide, Potassium, Calcium, Magnesium are in mmol/l; Albumin and Total proteins in g/dl and LDH in IU/l; Creatinine Clearance (CrCl) in ml/min. Table 11.1.8.3 Patients with missing metabolic parameters. Patient ID. Parameter Table 11.1.8.4 Other metabolic at baseline. Abnormalities grade ≥ 2 . Patient ID. **Parameter** Value Grade

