12.3.3. Other metabolic abnormalities

Table 12.3.3.1 Metabolic abnormalities during treatment, worst grade per patient

Parameter*	Gra	ade 1	Gra	de 2	Gra	de 3	Gra	de 4	Total (G1-G4)
rarameter.	N	%	N	%	N	%	N	%	N	%
Hyperglycemia										
(*) All metabolic	oaramet	ers susc	eptible t	o be gra	ded as p	er NCI-C	CTCAE	v4.0		

Table 12.3.3.2 Metabolic abnormalities during treatment, worst grade per cycle.

Parameter*	Gra	ade 1	Gra	de 2	Gra	de 3	Gra	de 4	Total (G1-G4)
rarameter.	N	%	N	%	N	%	N	%	N	%
Hyperglycemia										

^(*) All metabolic parameters susceptible to be graded as per NCI-CTCAE v4.0

Table 12.3.3.3 Metabolic abnormalities grade per cycle.

Doromotor*	Gra	ade 1	Gra	ide 2	Gra	ide 3	Gra	de 4	Total (G1-G4)
Parameter*	N	%	N	%	N	%	N	%	N	%
Hyperglycemia										
••••										

^(*) All metabolic parameters susceptible to be graded as per NCI-CTCAE v4.0

Table 12.3.3.4 Listing of patients and cycles with metabolic evaluations missing.

Patient ID.	Cycle	Lab. test
	 	 

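### SAP 8.2: the second corrected-calcium formula carries the wrong unit label (g/dl for mg/dl), and the correction is stated for hypocalcemia only although the tables also grade hypercalcemia

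*SAP*

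**What the plan says.** SAP 8.2 (Data analysis conventions) starts from the premise that "Calcium can be falsely low if hypoalbuminemia is present". For serum albumin below 4.0 g/dl it then states that "hypocalcemia will be reported after the following correction is performed". Two formulas follow. The first is in mmol/l and adds 0.2 for each g/dl by which albumin falls short of 4. The second is "Calcium corrected (g/dl) = Calcium (g/dl) + 0.8 x (4 - Albumin(g/dl", with a closing bracket. The convention is general: it is not limited to baseline or to treatment. It does not mention hypercalcemia.

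The tables look in both directions. The footnote to SAP Table 11.1.8.1 covers "Hyper and hypo abnormalities and all metabolic parameters susceptible to be graded as per NCI-CTCAE v4.0", and calcium is in the list that follows. For the treatment period, the footnotes in SAP 12.3.3 read "All metabolic parameters susceptible to be graded as per NCI-CTCAE v4.0". On units, the footnote to SAP Table 11.1.8.2 says "Units for Glucose, Sodium, Clorhide, Potassium, Calcium, Magnesium are in mmol/l" and gives albumin in g/dl. The SAP 12.3.3 shells state no units.

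Protocol 4.1 admits patients with "Albumin ≥ 25 g/l", which is 2.5 g/dl, so enrolled patients can fall under the 4.0 g/dl trigger.

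**The concern.** There are two separate problems in one short rule.

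First, the two formulas are meant to be one correction in two unit systems, so they must give the same answer. As labelled they do not. A formula in an analysis convention should be executable as printed.

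Second, the stated premise is that low albumin makes measured calcium read low. That artefact has two effects: it creates apparent hypocalcemia and it hides hypercalcemia. The rule addresses the first and is silent on the second, yet both are tabulated. If it is followed literally, false lows are removed and masked highs stay in, so the calcium rows of the metabolic tables would lean towards fewer abnormalities. At the least, two programmers could produce different hypercalcemia rows from the same text.

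**Working it through.** **Inputs**
- Molar coefficient: 0.2 mmol/l of calcium per g/dl of albumin (SAP 8.2).
- Mass coefficient as printed: 0.8 g/dl of calcium per g/dl of albumin (SAP 8.2).
- Trigger: albumin below 4.0 g/dl (SAP 8.2).
- Entry floor for albumin: 25 g/l = 2.5 g/dl (Protocol 4.1).
- Molar mass of calcium: 40.08 g/mol. This is a physical constant that the documents do not give.

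**Step 1: try to reproduce the second coefficient from the first**
- 0.2 mmol/l x 40.08 mg/mmol = 8.016 mg/l = 0.80 mg/dl = 0.00080 g/dl.
- The figure 0.8 is reproduced in mg/dl and not in g/dl.
- Ratio of printed to converted term: 0.8 / 0.0008016 = 998, or 1000 once 0.8016 is rounded to 0.8.
- Cross-check: for both lines to hold as printed, calcium would need a molar mass of 0.8 x 10 / 0.0002 = 40,000 g/mol. With mg/dl the same sum gives 0.0008 x 10 / 0.0002 = 40 g/mol.

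**Step 2: one value through each form (calcium 2.30 mmol/l, albumin 3.0 g/dl)**
- Molar form: 2.30 + 0.2 x (4 - 3.0) = 2.50 mmol/l.
- The same calcium in mass units: 2.30 x 40.08 / 10 = 9.22 mg/dl = 0.00922 g/dl.
- Second form applied in g/dl: 0.00922 + 0.8 x 1 = 0.809 g/dl, about 202 mmol/l.
- Second form applied in mg/dl: 9.22 + 0.8 x 1 = 10.02 mg/dl = 2.50 mmol/l, which agrees with the molar form.

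The coefficient is therefore right and the unit label is wrong.

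**Step 3: how far uncorrected calcium falls short**

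By the SAP's own molar formula, the shortfall is 0.2 x (4 - albumin).

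| Albumin (g/dl) | Shortfall (mmol/l) |
|---|---|
| 3.5 | 0.1 |
| 3.0 | 0.2 |
| 2.5 (entry floor) | 0.3 |

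As an illustration, a measured 2.50 mmol/l at albumin 2.5 g/dl corrects to 2.50 + 0.2 x 1.5 = 2.80 mmol/l. The measured value is chosen only for the example. No grade cut-off is applied, because the documents do not reproduce the CTCAE thresholds.

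**The case against.** The strongest reply is that little of this will reach a table.

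- **Units.** The baseline shell tabulates calcium in mmol/l and albumin in g/dl, which are the units of the sound formula. No shell shows calcium in g/dl. This stands, and it limits the first problem to the case where the second line is actually programmed with calcium in g/dl.
- **The label may correct itself in use.** A reader might infer that any calcium in conventional units would be ruined. It would not: 9 mg/dl at albumin 3 g/dl, entered directly, gives 9 + 0.8 = 9.8 mg/dl, which is right. An impossible result appears only if the value is first converted to 0.009 g/dl, giving 0.809 g/dl, or 809 mg/dl. That figure would be noticed.
- **The factor of 1000.** A reader might attach it to the corrected calcium as a whole. It belongs to the correction term only. In the example just given the final values differ by 809 / 9.8, about 83-fold.
- **Hypercalcemia.** A reader might infer that the plan is shown to under-report it. The SAP does not say that hypercalcemia is graded on uncorrected calcium; it is silent, and nothing forbids using the corrected value in both directions. Whether the CTCAE definitions would settle the matter cannot be checked from these documents. Under-reporting is thus a consequence of the literal reading, not an established fact. What remains is that the rule names one direction while the tables report two.
- **Safeguards.** Metabolic laboratory values are listed (SAP Listing 14.1.13). Laboratory abnormalities that are associated with clinically significant symptoms, or that lead to dose changes or significant added treatment, go to the adverse-event section of the case report form in any case (Protocol 9.2.1). Safety analysis is descriptive (SAP 7.4). These limit the harm but do not settle which calcium value is graded.

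**Conclusion.** Both parts hold, at low severity.

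The label error is certain, given only the molar mass of calcium: the second formula matches the first in mg/dl, and in g/dl its correction term is 1000 times too large. Its reach is conditional on someone programming that line with calcium in g/dl.

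The gap on hypercalcemia is real as a matter of text. If the silence is read as no correction, calcium used for grading hypercalcemia would be too low by 0.1 to 0.3 mmol/l for albumin between 3.5 and 2.5 g/dl, and some hypercalcemia could be missed in the safety tables. That conclusion rests on the literal reading and on the SAP's own premise and coefficient. The number of patients affected, and whether any grade would change, cannot be computed from the documents.

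Nothing here touches the response rate, the two-stage rule, the sample size or the error rates.

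**What to change.** In SAP 8.2, change the calcium unit in the second formula from g/dl to mg/dl on both sides of the equation, leaving albumin in g/dl. Then add one sentence: whenever albumin is below 4.0 g/dl, albumin-corrected calcium is used for grading both hypocalcemia and hypercalcemia. Because the convention is already general, that sentence will govern both the baseline and the on-treatment tables.

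The cost is one label and one sentence, with no new data and no change to the shells. The only downside is that some additional hypercalcemia grades may appear.
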